The Enjoying Work Collaborative^{13,80} began at ELFT and was subsequently led outside ELFT by the Royal College of Psychiatrists. Throughout England and Wales 38 teams in 16 healthcare organisations took part in the 12-month program in 2021-22. Led centrally, teams prioritised and worked upon locally important initiatives, supported by coaches, and informed by intermittent training via zoom. Weekly measures (for example of burnout using the Mini-Z scale) as well as before- and after- assessments (for example recommendations as this as a place to work) demonstrated some improvements. For example, staff who were extremely likely to recommend their team as a place to work increased from 31% to 41 %, while those with no symptoms of burnout increased from 24% to 33%. (Sample size varied each week). This work was conducted during the COVID-19 pandemic in the UK.

In New Zealand EDs, two initiatives are salient. From late 2020 members of our team led a pilot, known as Quality Improvement Learning System (QILS), in a single large volume NZ ED, that encouraged identification of problems and suggestions for improvement from frontline staff. In 6 months, 322 problems in ED care were identified, with solutions enacted for 176 (55%) (data unpublished). Staff feedback was generally positive, such as ease of use for highlighting on-the-floor problems by frontline staff.

A mechanism similar to QILS, to enable staff to identify problems and help with solutions, was introduced during the "migration" of a further single large volume NZ ED to a new building in late 2020.⁸¹ Staff were kept updated about the latest changes using feedback boards. A well-used system, in 6 months over 550 service improvement "tickets" were lodged electronically by staff. Issues were assessed in "huddles" by a dedicated team who decided upon the outcome (approve, investigate, or decline). Issues were then referred to the ED post-migration team for prioritisation, which depended on how quickly the issues could be resolved (ranging from immediate, achievable now to achievable within 1 year, to extensive work required). While the project was not formally evaluated, informal feedback about this improvement initiative was positive from staff, and departmental leaders want to re-institute a similar program in the future.

Our initial research

Quality Improvement in healthcare is challenging, and results of QI are often mixed.^{69,82} In addition to the content of any improvement initiative, how and within what context QI is implemented is important. An understanding of context, defined as "all factors that are not part of a QI intervention itself"⁸³ when planning, implementing, evaluating and researching QI initiatives is widely acknowledged as vital to success in QI.^{82,84-91} An ideal tool to assess our ED context would have been previously assessed for validity and reliability in NZ ED settings. No such tool exists to our knowledge.

Given the importance of context for workplace wellbeing and quality improvement, our initial research has focused on assessment of ED departmental capability for workplace wellbeing and improvement. A survey was undertaken. In order to assess NZ ED QI capability we modified questions and statements from the IHI self-assessment tool, the IR scale, and the ACEM Quality Standards Implementation Toolkit.⁹²⁻⁹⁴ No robust tool exists to assess ED-level workplace wellbeing capability. We based survey questions and statements upon the "era" of workplace wellbeing described by Shanafelt,⁶⁵ the Joy in Medicine Health System Recognition Program⁹⁵ and the ACEM Quality Standards Implementation Toolkit.⁹⁴

In September 2022, two senior (medical and nursing) staff from each ED in NZ were surveyed to clarify needs and capabilities. Of the 35 EDs in NZ with an annual census of >5000 patients, 59 staff from 29 EDs responded to the survey. In addition, staff were interviewed individually and in a focus group in October 2022. Interviews are ongoing, data are being analysed and are contributing to the refinement of small parts of our intervention. Results will assist with decisions about readiness for site enrolment in future research.

The intervention

*"Think of physician well-being as a three-legged stool. Improvement efforts should focus on all three domains to achieve best results."*³⁸

We propose a multicomponent intervention that addresses individuals' needs, is adaptable to local context, and that targets three organisation levels: the individual, the group/whānau, and the system. We hypothesise this intervention will reduce burnout and contribute toward the three areas NZ ED staff previously identified as beneficial to wellbeing, that is, a supportive team culture, provide professional development opportunities, and improve the provision of high-quality care.¹² This is described in detail in Methods.

Research Aims, Objectives, Hypothesis

The aim is to investigate if a multicomponent positive participatory organisational intervention aimed at improving the delivery of high-quality care, that is insider-led, includes the voice of frontline staff and accounts for complexity, will improve NZ ED staff burnout as determined by pre- and post-intervention assessment using the Copenhagen Burnout Inventory (CBI).

Hypothesis

Implementation of a multicomponent positive participatory organisational intervention will improve ED staff workplace wellbeing and burnout.

Table 7 Research Objectives

| |
|---|
| 
The Objectives of this research are to:
 
• Refine and use a multicomponent positive participatory organisational intervention package, based on individual, group and system-level components, in participating NZ EDs.• Undertake a before and after study of the multicomponent intervention package in NZ EDs, including:
○ A quantitative assessment of the intervention package on staff burnout, wellbeing, and ED quality measures.○ A mixed methods process evaluation of the intervention package examining fidelity and staff acceptability. |
|---|

Research Questions

Table 8 Research Questions

| |
|---|
| 
Primary research question:
 
• Does a multicomponent positive participatory organisational intervention package, based on individual, group and system-level components, improve burnout in NZ ED staff? 
Primary hypothesis:
 
• That a multicomponent positive participatory organisational intervention package improves workplace wellbeing, as determined by the CBI, in NZ ED staff. 
Secondary research questions:
 
• Does a multicomponent positive participatory organisational intervention package improve workplace wellbeing in NZ ED staff?• Does a multicomponent positive participatory organisational intervention package improve quality in ED systems?• Is a multicomponent positive participatory organisational intervention package feasible in a NZ ED setting? |
|---|

- Is a multicomponent positive participatory organisational intervention package acceptable to NZ ED staff?

Secondary hypotheses:

- That a multicomponent positive participatory organisational intervention package improves workplace wellbeing in NZ ED staff.
- That a multicomponent positive participatory organisational intervention package improves ED quality.
- That a multicomponent positive participatory organisational intervention package is feasible in a NZ ED setting.
- That a multicomponent positive participatory organisational intervention package is acceptable to NZ ED staff.

Methods

The Intervention

The intervention package will consist of three components targeting different levels of the HCO: the individual, the group, and the system. An initial Engagement visit to sites by the PI will involve presentations made to stakeholders and opportunities to discuss the intervention. A study start time will be established for each site in consultation with the Local Champions Group. It is anticipated that this will be within 2 months of the site Engagement visit. The intervention will take place over 12 months.

Individual-Level Component

Individual interventions must be acceptable, relevant and feasible for a given individual. An ability for participants to choose an intervention most acceptable to them is important.⁴⁷ Staff will be offered an opportunity to participate in an individual intervention. (Details and evidence for each are provided in the Individual-Level Interventions section). Participants will choose one of three possible interventions. These are:

- Three Good Things^{15,16,96}
 - Requires daily participation by writing down and considering what is going well in a participants life, and their role in that, for 15 days.
- Mindfulness⁵⁰
 - An online guided MBI for 10 minutes per day for 10 days.
- Looking forward¹⁶
 - An optimism/hope intervention that requires consideration of hoped-for future goals and experiences. Participants are prompted to engage 7 times over 28 days to consider and write about something they are looking forward to at different future time points.

Group-Level Component

Local Champions are key to the success of the program. In consultation with their local stakeholders, and mindful of acceptability and achievability, they will decide upon an intervention targeting the group as a whole. (Details and evidence can be found in the Whānau/Group/Culture/Team-Level Interventions section). LCs will choose one from the following:

- Clinical Event Debriefing (CED)¹⁸
 - Structured debriefing for all team members following important clinical events is challenging in a busy ED environment. Addressing barriers to implementation of usable debriefing tools is required for this to become embedded in ED culture.
- Learning from Excellence⁵⁸
 - A system which can effectively and efficiently capture and feedback to staff episodes of excellent care, as determined by peers, is required.

System-Level Component

This is aimed at improving the capability for all ED staff to engage in meaningful quality improvement. The Quality Improvement Learning System (QILS) is characterised by the following features:

- consumers and frontline staff highlight issues that affect quality of care.
- triage and prioritisation of those issues.
- allocation resource for work on prioritised improvement initiatives.
- staff participation and leadership in improvement work.
- feedback to staff and consumers.
- improvement training for staff.

While each feature of QILS will be adaptable to each context and informed by our recent research, the important characteristics will be present in all cases.

Improvement Training and Coaching

Training in Quality Improvement (QI) methods, with an emphasis on the local and ED contextual factors, will be delivered by an expert in QI training. Training will be delivered online. Individual and group coaching will be delivered by trained QI coaches. Monthly meetings of all LCG personnel will be opportunities to share lessons and build camaraderie required for sustainability. Further details of the training and coaching components are found elsewhere.

Local Champions Group

A Local Champions Group (LCG) will be critical to success at each site. The LCG will have up to 5 personnel and be a diverse composition of the local ED team, including one or more of senior doctors, nurses, other ED team members, consumers, and mana whenua. The LCG will be in the best position to understand local needs, liaise with local leaders, liaise with the investigators, and oversee many parts of the intervention in their ED. Each member of the LCG will attend the training and coaching program.

The study website

The study website provides a repository of important information for all those involved in the research. Established in 2020 and hosted by Squarespace, the website can be accessed via QR code or via the web address (www.woweated.com).

Access to open and password protected pages enables different groups access to relevant information. Participant information including about the various individual-level interventions will be available to participants, accessible via a QR code or the web address. Electronic links will allow participants to provide informed consent and access the intervention of their choice. In addition, Local Champions will have access to other information, for example group-level intervention information and links, and requirements for QI training and coaching.

The site will be maintained and modified by the PI, with advice from our University of Auckland IT specialist when required.

Study Design

A prospective multisite before and after study, using mixed methods, of the multicomponent intervention package in NZ EDs. The logistics of introducing a complex intervention into a series of EDs make compliance with randomisation, as in a randomised stepped wedge cluster study, impractical and unrealistic.

Study Setting

Individual NZ Emergency Departments will be the setting.

Site Selection

This intervention requires significant buy-in by all parties, particularly those in leadership positions within the ED and elsewhere within HCOs. Criteria for site selection are based on our previous research. As suggested by Shah,⁹⁷ and consistent with the theory of Diffusion of Innovations,⁹⁸ those departments that self-select, have relatively stable leadership, and are in the best position to make the required changes will be selected initially. It is hoped that feasibility and success at these "innovator" and "early adopter" sites will encourage an "early majority" to participate at a later date.

Eligibility Criteria for an Emergency Department to be a Study Site

Inclusion

1. Hospitals with an ED census of >5,000 presentations per year, (n=35 potential sites).
2. A LCG able to facilitate the implementation of the intervention.
3. Agreement from ED medical and nursing directors to support the intervention within current ED projects and to attempt to implement any suggested changes.
4. Ability to provide departmental data.
5. Executive agreement, at the directorate level and hospital level.
6. Locality approval for research

Exclusion

1. Be averse to implementing the intervention
2. Inability to provide departmental data.

Eligibility Criteria for individual staff to participate in research (answer surveys)

Inclusion

1. identify as a member of the ED staff and work there regularly
 - a. at least 1 shift per fortnight, or equivalent
2. current member of ED staff

Exclusion

1. ED is not considered primary place of work, outside the home

Outcome

Primary outcome

Mean change in CBI³ (work-related burnout domain) of all ED staff (nurse, doctor, other clinical, other non-clinical) 12 months post roll-out of intervention.

Secondary outcomes

Secondary outcomes are for all ED staff and each staff subgroup (nurse, doctor, other clinical, other non-clinical)

ED Staff

- Mean change in CBI (personal and patient-related domains) at 12 months.
- Utrecht Work Engagement Scale (UWES) 9-item short form⁹⁹ at 0 and 12 months.
- Psychological empowerment in the workplace¹⁰⁰ at 0 and 12 months.
- Mean change in WHO-5 Wellbeing Index (general wellbeing)¹⁰¹ at 12 months.

Department

- Number of issues raised via QILS
 - by staff
 - by patients, whānau and carers
- Number of QILS solutions
- Departmental demographics
 - patient census,
 - triage proportions,
 - triage time compliance,
 - admission rate,
 - intensive care unit (ICU) admission rate,
 - patient did not wait rates, and
 - ED length of stay (LOS) over intervention year.
 - Seasonally adjusted daily staff absence, vacancies, monthly resignations, and Bradford Scale Score.
 - Compliance with the 6 targets of Te Tumu Whakarae for Māori workforce development.¹⁰²

Participants

Sample Size

Power

Differences of ≥ 5 on the CBI work-related burnout scale are considered clinically significant.¹² A sample size of 900 staff participants over 8 EDs will have 90% power to detect a change of ≥ 5 (2-tail $\alpha=0.05$).

Recruitment

Site selection is discussed above. All staff at each study site are eligible for the interventions. Participation of staff will rely upon local champions. REDCap Public Survey Links for survey distribution to participants will be used to maximise usability, anonymity and the ability to collect data. Participation by staff will be voluntary.

Māori Participation

Recruiting and retaining a Māori ED health workforce is fundamental to the advancement of Māori health and are tenets of the Ministry of Health He Korowai Oranga framework, the ACEM Te Rautaki Manaaki Mana (Māori Health Strategy),⁶ and the Māori Workforce development targets agreed to by DHBs.¹⁰² While Māori are currently under-represented in the NZ ED workforce, by maximising workplace wellbeing and reducing burnout, staff and patients benefit, particularly Māori, who most stand to benefit by health systems that are responsive to Māori needs and healthcare aspirations now and far into the future. The team has active involvement of experienced Māori emergency care leaders in clinical care, advocacy and research.

Interventions that may benefit Māori staff and patients can be undertaken by participating individuals and departments. For example, an area for improvement related to Te Ao Māori may be identified by staff, and an improvement program undertaken.

Timeframe

Implementation

Two waves of implementation will begin in March 2023 and 2024 respectively. Each wave will have between three and five EDs. Lessons learned from wave 1 will inform the implementation of interventions in wave 2. The intervention and study periods will be for 12 months.

Data collection

Via RedCAP survey software. Staff survey at baseline (demographics: age range, gender,¹⁰³ work group, ethnicity,¹⁰⁴ years of experience at current ED) and 12 months of CBI and other measures. Routine ED data for triage compliance, did not wait rate, ED LOS, staff absence and resignations and Te Tumu Whakarae targets.

Analysis

Statistical methods

The primary and secondary outcomes will be compared pre and post intervention using a general linear mixed model with site as a random factor. Additional analyses of the primary outcome will be undertaken based on workforce group (nurse vs. other), and ethnicity (Māori vs. non-Māori), to test for differential effects of the intervention among these subgroups.

Longitudinal measurement of outcomes for individuals, that is, data-linkage and comparing results from the pre-and post-intervention surveys, is required for robust assessment of effects of the intervention. Balanced with the need for robust assessment is the need for participant confidentiality.

[figure not shown]
REDCap Public Survey Links for survey distribution to participants will be used to maximise usability, anonymity and the ability to collect data. The answers to the following two questions will be individually consistent, enabling data-linkage of coded participant data.

The screenshot shows two separate survey questions in a REDCap interface. The first question is 'What is the name of your first primary school' with a text input field. The second question is 'In which year was your mother born?' with a text input field. Both questions have a toolbar above them with icons for edit, copy, paste, and delete, and a label 'Variable: first_primary_school' and 'Variable: mother_birth_year' respectively. Below each question are buttons for 'Add Field', 'Add Matrix of Fields', and 'Import from Field Bank'.

Figure 1 Two data points for data linkage

A Public Survey Link will again be used to distribute the post-intervention survey. Respondents will be asked if they participated in the pre-intervention survey. All demographic questions will be the same as the pre-intervention survey.

The screenshot shows a survey question in a REDCap interface: 'Did you answer the QILS4WoWe@NZEDs survey in March 2023?'. A dropdown menu is open over the question, showing three options: 'Yes' (selected with a checkmark), 'No', and 'Unsure'. The question has a toolbar above it with icons for edit, copy, paste, and delete, and a label 'Variable: answered_survey_before'. Below the question are buttons for 'Add Field', 'Add Matrix of Fields', and 'Import from Field Bank'.

Figure 2 Post-intervention survey question about prior participation

The answers to the two questions that generate data points for data linkage questions (Figure 1) will be asked and can be matched and used to aggregate data from the pre- and post-intervention survey for analysis.

In the rare instance when data from these questions are not precise enough to discriminate between respondents, in addition, other demographic data will be used for data linkage. These will be questions about gender and profession.

Process Evaluation.

As well as understanding the direction and magnitude of effects of the proposed interventions, an understanding of what hindered and facilitated these effects, and how and why these effects occurred is important for a full understanding of the research.¹⁰⁵ We propose a process evaluation.

Data collected for the process evaluation will be quantitative, and include the following:

- Quantitative data relevant to the workings of the LCG will be collected in an excel sheet:
 - log of activities
 - training and coaching sessions provided
 - proportion of LCG attendance at each session
 - number of meetings
- Individual-level component of the intervention:
 - number of hits on website containing individual level intervention
- Group-level component of the intervention:
 - number of debriefs recorded; or
 - number of responses recorded
- System-level component of the intervention:
 - summary of:
 - problems identified,
 - solutions enacted,
 - effect of solutions.

Results will be anonymised by hospital.

Ethics and dissemination

Safety

All ED staff have access to Employee Assistance Programs. In addition, participants will be informed of and encouraged to seek help from other local sources, such as colleagues and participant's GP. Some departments also have a departmental psychologist who all staff can access.

Consent

Participant information will be available online prior to consent, as well as presented at engagement meetings. Electronic consent will be required of all participants prior to participation.

Confidentiality

No identifiable features will be captured via REDCap

Declaration of interests

No member of the research team has any conflicts to declare.

Access to data

Electronic data are stored in password-controlled computers and cloud storage. Data are accessible to the PI and statistician.

Dissemination policy

Dissemination of findings will primarily be through publication in peer-reviewed journals, and presentation at national and international hui and scientific meetings. Individual site feedback will be provided to each participating ED, and hospital executive leadership.

Further dissemination priorities will include:

- potentially national roll-out via the NZEMN if intervention successful
- potentially national roll-out via the HQSC to other hospital areas if intervention is successful
- writing commentaries and editorials in which the research findings can be further disseminated, via established links with international journals, and
- presenting findings to lay audiences through established media links.

References

1. HQSC. Engaging With Consumers. A guide for district health boards. Health Quality & Safety Commission, 2015.
2. WHO. ICD-11. (<https://icd.who.int/browse11/l-m/en#/http://id.who.int/icd/entity/129180281>).
4. ACEM. Standard Terminology for Emergency Departments Policy (P02). Australasian College for Emergency Medicine; 2019.
5. ACEM. Quality Standards for Emergency Departments and Hospital-Based Emergency Care Services. <https://acem.org.au/Content-Sources/Advancing-Emergency-Medicine/Better-Outcomes-for-Patients/Quality-Standards2022>.
6. ACEM. Te Rautaki Manaaki Mana Excellence in Emergency Care for Māori. 2019.
8. HQSC. Mō mātou About us Health Quality and Safety Commission. (<https://www.hqsc.govt.nz/about-us/>).

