This will be a location for sources of information for all stakeholders.

Our diverse team has considerable experience and success with research.

Introduction

Background

Aside from primary care, emergency medicine (EM) is the specialty with which New Zealand (NZ) health consumers have the greatest interaction, with over 1 million consultations in NZ annually. Central to the delivery of high-quality EM care are emergency department (ED) staff, who need to function optimally in order to deliver high-quality healthcare: that which is safe, timely, effective, equitable, patient-centred and efficient.^{20,21} Yet functioning optimally is not easy in EDs, which are complex, time poor, time-pressured environments, where staff must make rapid decisions, sometimes life and death, often when patients and whānau are at their most vulnerable. EDs provide a "perfect storm" for burnout, a long-term stress reaction defined by emotional exhaustion, depersonalisation, and a lack of sense of personal accomplishment.

Healthcare staff wellbeing is a prerequisite for high-quality healthcare and has advantages for legal, ethical, fiscal, and patient outcomes.^{20,22-26} Staff with high burnout have higher turnover, increased absenteeism, and make more errors. Patients rate communication by staff with higher burnout poorly, and overall patient satisfaction is lower. Hospitals with higher burnout scores have higher avoidable infection rates.²⁰ EM physicians with burnout practice suboptimal care including providing inadequate analgesia, over-testing and unsafe discharging practices.²⁷

Staff wellbeing is recognised internationally as an organisational priority for healthcare systems.^{20,28} Frameworks for delivery of high value healthcare, such as the 'quadruple aim,' recognise the core role that healthcare staff play in providing high-quality care with the overarching goals of improving individual care; improving population health; reducing per capita healthcare cost; and improving the experience of providing care. In NZ the Health Quality and Safety Commission (HQSC) have recognised the threat poor workforce wellbeing poses with respect to errors and low-value healthcare delivery,²³ while within EM, accreditation bodies such as Australasian College for EM (ACEM) have made staff wellbeing a key priority.²⁸

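### The protocol calls individual linkage required, but its primary outcome and stated model do not use it, so workforce turnover can enter the pre-post estimate

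*Protocol*

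**What the plan says.** Under Outcome, Primary outcome, the protocol takes the mean change in the CBI work-related domain "of all ED staff (nurse, doctor, other clinical, other non-clinical) 12 months post roll-out of intervention". Individual eligibility for the surveys requires the respondent to be a "current member of ED staff". Both surveys go out by open link; for the second, "A Public Survey Link will again be used to distribute the post-intervention survey".

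Under Analysis, Statistical methods, the outcomes are to be "compared pre and post intervention using a general linear mixed model with site as a random factor". No participant term is named. The next paragraph says: "Longitudinal measurement of outcomes for individuals, that is, data-linkage and comparing results from the pre-and post-intervention surveys, is required for robust assessment". Two linkage questions are collected for this purpose, and the matched answers "can be matched and used to aggregate data from the pre- and post-intervention survey for analysis". The second survey also asks about participation in the first. Data collection includes years of experience at the current ED.

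Study Design describes an uncontrolled before-and-after study. The Background says: "Staff with high burnout have higher turnover, increased absenteeism, and make more errors". Sample Size takes 5 points on the work-related scale as clinically significant.

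**The concern.** The protocol says what a robust assessment needs and then states an outcome and a model that do not supply it. Someone who leaves during the year can answer only the first survey. Someone who joins can answer only the second, after partial exposure. If all responses enter a model with period and site, the period coefficient is in essence a site-weighted difference between two partly different groups. Linking the records without a participant term leaves that difference essentially unchanged.

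The protocol supplies a mechanism for the groups to differ in burnout, and no control group offsets it. The text also leaves room to choose between all respondents and linked respondents after the data are seen. As the working shows, those two choices can differ in sign when the intervention does nothing.

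**Working it through.** **The plan's own figure.** The protocol gives no figure for turnover. The nearest is 90% power with 900 staff for a 5-point change, two-sided alpha 0.05. Table 5 gives an SD of 19.1 but does not tie it to the power calculation. With that SD, 90% power needs 2 × 19.1² × (1.96 + 1.2816)² / 5² = 307 per survey, 614 in total. Without clustering, 450 against 450 gives 97.5% and 900 against 900 gives 99.98%. The 90% is not reproduced because its inputs are not stated, and it does not bear on this point either way.

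**Inputs for the turnover check.**
- From Table 5: mean 49.9, SD 19.1.
- Assumed: 20% leave; the odds of leaving rise 1.5-fold per SD of baseline score; pre-post correlation 0.5; no intervention effect, so the baseline workforce would still average 49.9 at 12 months had nobody left.
- Joiners' mean is unknown and is varied.

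**Step 1, who leaves.** Under these odds, leavers average about 55.9 and stayers about 48.4 at baseline. Check: 0.2 × 55.9 + 0.8 × 48.4 = 49.9.

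**Step 2, stayers at 12 months.** Stayers regress towards the mean: 49.9 + 0.5 × (48.4 - 49.9) = 49.15.

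**Step 3, all respondents.** Shift = 0.8 × 49.15 + 0.2 × J - 49.9, where J is the joiners' mean.

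| Joiners' mean J | Shift in points |
|---|---|
| 40 | -2.58 |
| 45 | -1.58 |
| 49.9 | -0.60 |
| 55.9 (as leavers) | +0.60 |

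The shift is zero at J = (49.9 - 39.32) / 0.2 = 52.9, so joiners above that value reverse the direction.

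**Step 4, linked completers only.** 49.15 - 48.4 = +0.75, about +0.8, which is against the intervention.

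**Step 5, likelihood-based estimate keeping baseline-only respondents.** Simulation under the same assumptions gave about 0.0.

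**Step 6, against significance.** With 900 responses at each survey and no clustering, SE = 19.1 × √(2/900) = 0.90, so a shift of 1.96 × 0.90 = 1.76 is declared significant. In simulation the all-respondent contrast gave a significant false improvement in about 5%, 40% and 86% of runs for J = 49.9, 45 and 40. The nominal rate in that direction is 2.5%.

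**Range.** With 10% leaving, 1.25-fold odds and J = 49.9, stayers start at about 49.5 and reach 49.7: 0.9 × 49.7 + 0.1 × 49.9 - 49.9 = -0.2. With 30% leaving, 2-fold odds and J = 40, stayers start at about 46.3 and reach 48.1: 0.7 × 48.1 + 0.3 × 40 - 49.9 = -4.2.

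**The case against.** The strongest reply is that the linkage plan already answers the concern. The primary outcome is a mean change, which fits within-person change. The reference to all ED staff may only mean that occupations are pooled, since the secondary outcomes then separate them. The model sentence does not say that site is the only term, and participant effects and the handling of unlinked records may be set out in an SAP that is not shown.

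Much of this stands. A reader might infer that the protocol fixes a comparison of everyone present at each survey. It does not: the linkage text points the other way. What remains is that the protocol states linkage as a requirement and then states an outcome and model that do not carry it through. That is a mismatch in the current text, not detail properly deferred.

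A reader might also infer a certain bias towards improvement, sized as the share leaving times the gap between leavers and stayers, here 0.2 × (55.9 - 48.4) = 1.5 points. The documents do not support this. That product ignores stayers' regression to the mean and takes joiners to score like stayers. Turnover also predates baseline, and in a steady workforce the mean need not move at all.

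Finally, the choice between stayers and the whole department is partly one of purpose. All staff are eligible for the intervention, and resignations and vacancies are themselves secondary outcomes.

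**Conclusion.** The point holds in this form: as written, the primary outcome and model leave the required linkage unused and let workforce change enter an uncontrolled primary estimate. Improvement is the likely direction but not a certain one, because it depends on joiners' scores, which the documents do not give.

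Under the central assumptions (20% leaving, 1.5-fold odds per SD, correlation 0.5) the shift is about -0.6 to -2.6 points for joiners averaging 49.9 to 40. Across the wider assumptions worked above it runs from -0.2 to -4.2, and it becomes positive if joiners average more than 52.9. It would be too strong to conclude that turnover alone yields a 5-point effect: none of these cases reaches it. The threat is to the significance test and to the size of the estimate. Restricting to linked completers is not a safe default either, at about +0.8.

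The near-zero bias of the likelihood-based analysis holds if leaving depends on the observed baseline score. Leaving driven by unrecorded worsening during the year would still bias it.

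**What to change.** In Analysis, Statistical methods:
- State the primary model as a likelihood-based mixed model with participant nested in site, using the linkage codes and keeping respondents who answered only at baseline.
- Identify staff who joined after roll-out by tenure of under one year at the current ED at the 12-month survey. Leave them out of the primary contrast and report them separately. Do not use a No to the prior-participation question for this: long-serving, fully exposed staff who skipped baseline also answer No.
- Report baseline CBI for linked and unlinked respondents.
- Give the all-respondent comparison, adjusted for work group and tenure, as a sensitivity analysis.

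Align the primary outcome wording with this population. The change is to wording only, as every field is already collected. The primary result would then apply to staff employed at roll-out, not to the whole department at 12 months, and imperfect linkage costs some precision. That cost looks bearable: ignoring clustering, with SD 19.1, 90% power for 5 points needs 2 × (1 - r) × 19.1² × (1.96 + 1.2816)² / 5² linked pairs, which is 215, 154 or 92 at an assumed correlation r of 0.3, 0.5 or 0.7.
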